### **8.3. Screen Failures**

Screen failures are defined as participants who consent to participate in the clinical study but are not subsequently assigned to study intervention/entered in the study. A minimal set of screen failure information will be collected, including demography, screen failure details, eligibility criteria, and any AE or SAE.

Individuals who do not meet the criteria for participation in this study (screen failure) may be rescreened once, with the approval of the medical monitor. Rescreened participants will be assigned a new participant number.

## **8.4. Investigational Product Discontinuation and Early Termination from the Study**

A participant may withdraw from the study at any time at his/her own request for any reason. The investigator may discontinue a participant from the study and/or from IP for safety, behavioral, compliance, administrative reasons. When a participant is discontinued from IP, the participant should continue, if willing, to participate in the remainder of the study by attending all scheduled visits per the SOA.

The reason for IP discontinuation and/or the reason for early termination from the study must be documented in the participant's study record and recorded in the participant's electronic case report form (eCRF).

The investigator must notify the sponsor and/or the medical monitor when a participant stops participation in the study for any reason.

### **8.4.1. Investigational Product Discontinuation**

Participants who discontinue IP will be invited by the investigator to complete all of the scheduled study visits and assessments through the end of the Treatment Period. Those who decline to continue participation will be asked to complete an ET Visit.

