## 7. INVESTIGATIONAL PLAN

### 7.1. Overall Study Design

This is a randomized, placebo-controlled, double-blind study to evaluate the cognitive effects, safety, tolerability, [REDACTED] of SAGE-718 in participants with premanifest or early manifest HD. Participants will be adults with genetically confirmed expansion of the Huntington (HTT) gene cytosine, adenine, and guanine (CAG) trinucleotide repeat at screening who meet diagnostic criteria detailed in the inclusion criteria below (including UHDRS scores and CAG-Age-Product [CAP] scores within specific ranges).

An adult study partner is optional but highly recommended for each participant to support completion of study activities and to answer questions about the participant's condition. For prospective participants and study partners (if applicable), the study will begin with the informed consent process.

Screening, safety, and efficacy will be performed according to the schedule presented in [Table 2](#), [REDACTED] will be performed according to the schedule presented in and [Table 3](#).

Screening assessments will be performed to determine eligibility. Participants and study partners (if applicable) will receive training on the study procedures and devices.

Eligible participants will be randomized 1:1 to receive either SAGE-718 (1.2 mg at Day 1 visit through the day prior to Day 28 visit and 0.9 mg from Day 28 visit until End of Treatment [EOT]) or placebo for 84 days. Beginning on Day 1 and continuing through Day 84, participants will self-administer blinded investigational product (IP) once per day in the morning. IP administration will be monitored via a medication adherence monitoring platform used on smartphones to visually confirm IP ingestion. At clinic visits, participants will take the IP under staff supervision, followed by assessments of cognitive function, [REDACTED]

[REDACTED]. Study staff will dispense sufficient IP for daily administration until the next scheduled study visit. Adherence to the dosing regimen will be assessed at each in-clinic visit by review of the medication adherence monitoring platform, examination of the used packaging, and counting any returned tablets.

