During the Treatment Period, participants will be able to receive IP as long as there are no dose limiting safety/tolerability concerns. Participants who cannot tolerate 1.2 mg will receive 0.9 mg for the remainder of the Treatment Period. At the discretion of the investigator, participants who cannot tolerate the 0.9 mg dose will be discontinued from IP. Participants who discontinue IP early should complete the remaining study visits as scheduled unless the participant withdraws consent or loses the capacity to grant consent. If a participant withdraws from the study/stops study participation early, an early termination (ET) visit should be conducted. Treatment with SAGE-718 can be ended without down titration.

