### **7.1.3. Follow-up Period**

Follow-up period starts after Day 84 and continuing through Day 112. After completing the Treatment Period, participants will return to the clinic for follow-up visits on Days 98 and 112 (or ET) to collect continued safety and efficacy data.

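### Protocol 8.4.1 invites participants who stop IP to visits only up to Day 84, while four other places keep them to Day 112; read literally, it ends scheduled safety follow-up 28 days sooner

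*Protocol*

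**What the plan says.** Five places say how long a participant who stops IP stays in the visit schedule.

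- Protocol 8.4.1: the participant is invited to "complete all of the scheduled study visits and assessments through the end of the Treatment Period". The next sentence covers refusals: "Those who decline to continue participation will be asked to complete an ET Visit".
- Protocol 8.4, its parent section: the participant should continue, if willing, "to participate in the remainder of the study by attending all scheduled visits per the SOA".
- Protocol 7.1: "Participants who discontinue IP early should complete the remaining study visits as scheduled", with exceptions for withdrawn consent and lost capacity to consent. The synopsis and SAP 5.1 carry the same sentence.

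The two end points differ. Protocol 7.1.3 states: "Follow-up period starts after Day 84 and continuing through Day 112". It places the Day 98 and Day 112 visits in that period, so the end of the Treatment Period cannot be read to include them.

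Other provisions set what depends on the last visit:

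- Protocol Table 2 collects AEs for as long as the participant takes part.
- SAP 8.4.2, 8.4.3 and 8.4.4 summarise potentially clinically significant laboratory, QTcF and vital-sign values in the 28 days after the last dose.
- SAP 8.4.1 counts a TEAE as on-treatment up to 30 days after the last dose.
- SAP 8.2.1 defines study completion by the Day 112 visit.

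**The concern.** Protocol 7.4 sends sites to Section 8.4 for what to do when IP is stopped early. There they find the full-schedule rule and, directly beneath it, a subsection with a nearer end point. Two sites could treat identical participants differently, and each could cite the protocol.

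At stake is the length of off-drug safety observation. The proportion of participants with TEAEs is the named safety endpoint, and TEAEs can be counted only while they are collected. A participant released at Day 84 after stopping on Day 80 has four days off drug, against a nominal 28 for someone who finishes treatment. After the follow-up ends, SAEs are reportable only if judged related (Protocol 12.2.6). A participant who did everything 8.4.1 asked would also be reported as not having completed the study.

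**Working it through.** **Inputs.** Last scheduled dose and end of the Treatment Period: Day 84 (Protocol 7.1, 7.1.3). Last follow-up visit: Day 112 (7.1.3). Visit windows: ±2 days (Table 2). Post-dose periods: 28 days (SAP 8.4.2 to 8.4.4) and 30 days (SAP 8.4.1).

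**The plan's own figure.** For a participant who completes treatment, 112 − 84 = 28 days, which matches the SAP's 28-day follow-up period. With visit windows the range is 110 − 86 = 24 to 114 − 82 = 32 days.

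**Early stoppers.** For a last dose on Day d, off-drug observation is 84 − d under a literal 8.4.1 and 112 − d under the other four places. The difference is always 28 days.

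| Last dose, Day d | 84 − d | 112 − d |
|---|---|---|
| 54 | 30 | 58 |
| 56 | 28 | 56 |
| 57 | 27 | 55 |
| 70 | 14 | 42 |
| 80 | 4 | 32 |
| 83 | 1 | 29 |

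**Against the 28-day period.** 84 − d < 28 when d > 56, so last doses on Days 57 to 83 fall short. Under the full schedule the shortest case is Day 83, with 29 days, so no early stopper has less than a completer's nominal 28.

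**Against the 30-day TEAE period.** 84 − d < 30 when d > 54. This yardstick needs care: a completer's nominal 28 days also falls short of 30, so the 28-day comparison is the fairer one.

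**Which scheduled measurements are lost (nominal days, unredacted rows of Table 2).**

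- Day 112 laboratory tests and ECG fall 112 − d days after the last dose. That is 28 or fewer only if d ≥ 84, so for early stoppers these values lie outside the 28-day summaries under either rule. They still feed the by-visit and last-value-on-study summaries.
- Day 98 vital signs fall 98 − d days after the last dose, which is 28 or fewer when d ≥ 70. The 28-day vital-sign summary therefore loses a reading for last doses on Days 70 to 83.
- New AEs arising after Day 84 are lost to scheduled collection for every stopper whose visits end there.

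**The case against.** The strongest reply is that 8.4.1 is an invitation, not a limit. It neither ends participation nor bars Days 98 and 112, and a site that follows 8.4 also satisfies 8.4.1. That stands. A reader might infer that the passages cannot all be followed; they can. The defect is that they permit different last visits.

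The second reply is that other provisions protect safety follow-up, and much of it stands:

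- A reader might infer from the refusal sentence in 8.4.1 that someone who attends to Day 84 gets neither the Day 112 nor the ET assessments. Protocol 8.4.2 asks for an ET visit, where possible, whenever a participant stops taking part. Day 84 also has its own laboratory tests, ECG, vital signs, brief physical examination and pregnancy test, which are already off-drug for an early stopper. However, an ET visit at about Day 84 adds no observation time.
- Participants stopped for an AE are followed until it resolves, stabilises or is no longer clinically significant (12.2.1). Suspected seizure and potential Hy's Law cases have their own follow-up (7.4.1, 12.2.7). These rules cover the known event, not new ones.

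The third reply is that four places state the full schedule, including the opening paragraph of 8.4, so few sites may release anyone at Day 84. The documents do not settle how sites would act.

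**Conclusion.** The inconsistency is real and should be corrected. Its size is 28 days of scheduled follow-up for each participant whose site follows 8.4.1 literally. Off-drug observation drops below the completers' nominal 28 days only for last doses on Days 57 to 83. The loss is mainly of new AEs after Day 84 and the second set of off-drug assessments, and these participants are not completers under SAP 8.2.1. The day counts assume visits on nominal days and no contact after Day 84.

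Three stronger readings are not supported:

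- That everyone who stops IP is observed for less time than completers. Anyone whose last dose is on or before Day 56 has at least 28 days even under 8.4.1.
- That TEAE proportions are biased in favour of SAGE-718. This would need more stopping, at the relevant times, in that arm and literal use of 8.4.1; the documents give no discontinuation rate by arm.
- That the planned 20% dropout gives the number affected. It is a sample-size allowance, and the documents say neither how many would stop IP yet stay in the study nor when.

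The Day 84 primary endpoint and the treatment policy strategy are untouched, because both rules reach Day 84.

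**What to change.** Reconcile Protocol 8.4.1 with the synopsis, Protocol 7.1 and 8.4, and SAP 5.1, so that one last scheduled visit is stated for participants who stop IP. Send sites a short memo giving it. The choice of rule is the sponsor's; as a matter of text, 8.4.1 stands alone against the other four places.

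If the places are aligned on the full schedule, the cost is one phrase in 8.4.1 plus the memo, since the Day 98 and Day 112 visits already exist. If they are aligned on Day 84, the other four places would have to change, and the SAP's completion definition and 28-day summaries would need review for these participants.

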### **8.4.2. Early Termination from the Study**

At the time of study withdrawal/stopping study participation, if possible, an ET visit should be conducted. The participant will be permanently discontinued both from the IP and from the study at that time.

If the participant withdraws consent for disclosure of future information, the sponsor will retain and continue to use any data collected before such a withdrawal of consent.

If a participant withdraws from the study, he/she may request destruction of any samples taken and not tested, and the investigator must document this in the site study records.

Possible reasons for study discontinuation include but are not limited to the following:

- AE
- Pregnancy
- Protocol deviation
- Non-compliance with study drug
- Lost to follow-up
- Withdrawal by subject
- Screen failure
- Study terminated by sponsor
- Physician decision
- Other

#### **8.4.3. Loss to Follow-up**

A participant will be deemed lost to follow-up after 3 attempts at contacting the participant have been made and it has been at least 1 month since the last participant contact. All attempts at contact and the reason for discontinuation will be documented. If the investigator becomes aware of a change in the participant's status or receives more information about a participant's disposition, this information will be documented.

#### **8.4.4. Replacement of Participants**

Participants who discontinue or withdraw from the study will not be replaced. However, additional participants may be randomized and dosed to ensure a sufficient number of evaluable participants or if the early discontinuation rate is higher than expected.

## **9. TREATMENT OF PARTICIPANTS**

### **9.1. Description of Investigational Product**

SAGE-718 oral softgel lipid capsules are opaque, white to off-white, oval capsules containing either 0.3, 0.6, 0.9, or 1.2 mg of SAGE-718 drug substance.

### **9.2. Prior Medications, Concomitant Medications, Restrictions, and Contraception Requirements**

#### **9.2.1. Prior and Concomitant Medications and/or Supplements**

All medications and supplements taken within 8 weeks prior to Screening, all medications used to treat HD (including anti-sense oligonucleotide [ASO] therapies) regardless of timing, and all nonpharmacological methods (eg, psychosocial, psychotherapeutic) used to treat or prevent neuropsychiatric, functional, and cognitive manifestations of HD are to be recorded.

Information regarding diagnosis, isolation, and/or hospitalization due to coronavirus disease 2019 (COVID-19) will be documented as part of medical history, AE collection, and prior/concomitant medication/procedure collection at Screening and throughout the study.

At visits subsequent to Screening, all changes to any medication should be captured. All medications and/or supplements taken from the first dose of IP through the final study visit (including start and end dates, route, dose/units, frequency, and indication) will be recorded on the. Any concomitant medication determined necessary for the welfare of the participant may be given at the discretion of the investigator at any time during the study.

Because this study aims to measure effects on cognitive performance, it is important to evaluate single or combined concomitant medications and their doses for their potential effects on cognition. Investigators will carefully review concomitant medications for possible cognitive effects at Screening to determine participant eligibility and throughout the study.

#### **9.2.2. Prohibited Medications**

Prohibited medications prior to and during the study include:

- Gene therapy
- HD investigational drug, biologic, or device within 180 days prior to Screening and until the final visit
- Non-HD investigational drug, biologic, or device within 30 days or 5 half-lives (whichever is longer) prior to Screening and until the final visit

Use of the following medications is prohibited within 30 days of screening and during the entire course of the study:

- Medications that inhibit cholesterol absorption (eg, ezetimibe).
- Bile acid sequestrants (eg, colestevam, colestipol, cholestyramine).
- Medications with potent effects at the NMDA receptor, including memantine, amantadine, cycloserine, ketamine, or related compounds.

- THC-containing substances (any route of administration), regardless of whether or not they are prescribed

Any medication determined necessary for the welfare of the participant may be given at the discretion of the investigator at any time during the study; however, the use of any prohibited medications will be captured as a protocol deviation.

### **9.2.3. Other Restrictions and Recommendations**

Participants must agree to refrain from drugs of abuse for the duration of the study (unless deemed by the investigator to reflect a prescribed medication) and from alcohol during the 48 hours preceding each study visit.

Psychotropic medications and medications that are known to affect cognitive performance (eg, antidepressants, anxiolytics, stimulants, benzodiazepines, antipsychotics, anticholinergics) must be at a stable dose for at least 30 days prior to the first IP administration. Additions and/or modifications to these medications should be minimized throughout the course of the study.

Other medications given at doses, frequencies, or in combinations that are likely, in the opinion of the investigator, to have a deleterious effect on cognitive performance are to be avoided as much as possible.

Any additions or modifications to medications during the course of the study will be recorded in the concomitant medications log and source documentation.

### **9.2.4. Acceptable Forms of Contraception**

As per the Clinical Trials Facilitation and Coordination Group (CTFG), a female is considered of childbearing potential (FOCBP) eg, fertile, following menarche and until becoming postmenopausal unless permanently sterile. Permanent sterilization methods include hysterectomy, bilateral salpingectomy and bilateral oophorectomy.

A postmenopausal state is defined as no menses for 12 months without an alternative medical cause and confirmed by follicle-stimulating hormone (FSH)  $> 40$  mIU/mL. A high FSH level in the postmenopausal range may be used to confirm a postmenopausal state in females not using hormonal contraception or hormonal replacement therapy. However, in the absence of 12 months of amenorrhea, a single FSH measurement is insufficient.

A male is considered fertile after puberty unless permanently sterile by bilateral orchidectomy.

Acceptable forms of highly effective contraception (eg, can achieve a failure rate of  $<1\%$  per year when used consistently and correctly) for participants of childbearing potential or for a male participant's partner of childbearing potential include:

- Sexual abstinence
- Combined (estrogen and progestogen containing) oral, intravaginal, or transdermal hormonal contraception associated with inhibition of ovulation;
- Oral, injectable, or implantable progestogen-only hormonal contraception associated with inhibition of ovulation;
- Intrauterine device;

- Intrauterine hormone-releasing system;
- Bilateral tubal ligation or bilateral tubal occlusion (performed at least 3 months prior to Screening);
- Vasectomized partner (performed at least 3 months prior to screening) (Note: vasectomized partner is a highly effective birth control method provided that partner is the sole sexual partner of the participants of childbearing potential and that the vasectomized partner has received medical assessment of the surgical success.)

Acceptable forms of contraception for male participants include:

- Sexual abstinence;
- History of vasectomy (performed at least 3 months prior to Screening);
- Condom with spermicide used together with highly effective female contraceptive methods if the female partner(s) is of childbearing potential (see above for list of acceptable female contraceptive methods).

### **9.3. Intervention After the End of the Study**

Not applicable.

### **9.4. Treatment Adherence**

Beginning on Day 1 and continuing through Day 84, participants will self-administer blinded IP once per day in the morning. IP administration will be monitored via a medication adherence monitoring platform used on smartphones to visually confirm IP ingestion. At clinic visits, participants will take the IP under staff supervision, followed by assessments of cognitive function, [REDACTED]. Study staff will dispense sufficient IP for daily administration until the next scheduled study visit. Adherence to the dosing regimen will be assessed at each in-clinic visit by review of the medication adherence monitoring platform, examination of the used packaging, and counting any returned tablets. This information will be documented in the source files and eCRF, along with any deviations from the prescribed dosage regimen. Details about IP accountability are included in Section 10.6.

### **9.5. Randomization and Blinding**

This is a randomized, placebo-controlled, double-blind study. Eligible participants will be randomized 1:1 to receive either SAGE-718, or placebo for 84 days.

Participants, clinicians, and the study team will be blinded to treatment allocation. Randomization will be performed centrally via an interactive response technology (IRT) system. Randomization schedules will be generated by an independent statistician. The allocation to treatment group will be based on the randomization schedule. The randomization schedules will be kept in a secure place, accessible only to authorized personnel until the time of study unblinding. The blinding of the study will be broken after the database has been locked.

Database lock will occur in 2 parts (see Section 13). A selected team of Sponsor personnel will be unblinded after Part 1 of database lock to conduct Part 1 data analyses, but site personnel, participants, and other Sponsor personnel will remain blinded until after Part 2 of database lock.

### **9.5.1. Emergency Unblinding**

During the study, the blind can be broken by the investigator via the IRT system only when the safety of a participant is at risk and the treatment plan is dependent on the study treatment received. Unless a participant is at immediate risk, the investigator should make attempts to contact Sage prior to unblinding the study treatment administered to a participant. The responsibility to break the treatment code in emergency situations resides solely with the investigator. If the unblinding occurs without Sage's knowledge, the investigator must notify Sage within 24 hours of breaking the blind. All circumstances surrounding a premature unblinding must be clearly documented in the source records.

In all cases where the study personnel are unblinded, pertinent information (including the reason for unblinding) must be documented in the participant's source documentation and on the eCRF. At the time of withdrawal from the study/stopping participation, if possible, an ET visit should be conducted.

## 10. INVESTIGATIONAL PRODUCT MATERIALS AND MANAGEMENT

### 10.1. Investigational Product

SAGE-718 softgel lipid capsules are opaque, white to off-white, oval capsules containing 0.3, 0.6, 0.9, or 1.2 mg of SAGE-718 drug substance. The capsules are composed of SAGE-718 drug substance, butylated hydroxyanisole, gelatin, glycerin, glyceryl monocaprylate, glyceryl monolinoleate, lecithin, medium chain triglycerides, purified water, sorbitol, titanium dioxide, and vitamin E polyethylene glycol succinate as excipients.

